**Statistical Analyses:** All hypotheses will be two-sided at the 0.05 level and intent-to-treat with data included for all subjects completing at least one post-baseline assessment. Data analyses will employ generalized additive mixed models (GAMMs) tailored for longitudinal data. GAMMs allow for potentially nonlinear effects of independent variables on outcomes; the nature of the nonlinearity and degree of smoothness is data-determined for each independent variable. Models will include as covariates variables that differ significantly by condition. We will use Akaike Information Criterion (AIC) to determine covariance structures and variable selection. To control for inflated Type I error rates from multiple testing within each hypothesis, we will use the Westfall-Young step down maxT randomization procedure, which adjusts p-values for significance in multiple comparisons while taking into account the correlation of the outcomes. In this way we can control for an overall family-wise error rate of .05 while achieving more power than Bonferroni adjustments. **Missing Data:** Follow-up data will be obtained on all participants, regardless of treatment completion. We will perform sensitivity analyses for impact of potentially informative missing data via pattern mixture models extended to incorporate random effects. We anticipate 15% dropout between each time point, accounting for an overall (cumulative) dropout rate of 39%.

**Hypothesis testing: Hypothesis 1:** Caregivers receiving mPEP will report reduced depression, improved positive affect, reduced negative affect, and improved well-being compared to caregivers receiving a web-based bibliotherapy intervention. **Dependent Variables:** Depressive Symptoms, Positive and Negative Affect; SF-36 scores. **Independent Variables:** Condition and Time (Baseline, 3-, 9-, and 15-months). **Statistical Analysis:** This hypothesis will use GAMMs. Condition will be entered as a fixed-effect predictor along with time and their interaction. If the smoothed interaction of condition x time is significant at the .05 level (determined by an F test of relevant coefficients in the model) we will test for pairwise differences with Westfall-Young adjusted p values.

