**Power Analysis:** Because the mPEP intervention is based upon our in-person version of PEP for caregivers, we anticipate effect sizes to be comparable to those seen in our previous trials. Accordingly, we powered our study based results showing an effect size of 0.4 (small to moderate) in favor of mPEP with an active comparator. Sample size estimates were based on the Hedeker, et al. method for various covariance structures for mixed effects models. For the proposed study, we assumed an autoregressive covariance structure, with a correlation between sequential assessments set at 0.5 based on our previous trial in caregivers. Using this methodology, assuming an alpha level of 0.05, we have a minimum 90% power to detect an effect size of 0.4 with 15% attrition between each time-point (39% cumulative drop-out rate), when there are 100 subjects per each condition.

**Hypothesis 2:** Greater treatment-associated change in behavioral activation will be associated with greater improvement of caregiver well-being outcomes.

**Statistical Analysis:** For this hypothesis, multilevel (mixed) models will be used. To test for mediation, we will utilize the analytic strategy described by Krull and MacKinnon. In this approach, four conditions are tested: a) the relationship between intervention condition and the dependent variables (e.g. Depressive symptoms), b) the relationship between intervention condition and mediator (behavioral activation), c) the relationship between behavioral activation and the outcome, and d) the relationship between intervention condition and outcome after controlling for the proposed mediator. Mediation will be tested using the Monte Carlo Method for Assessing Mediation (MCMM). **Power Analysis:** The proposed study will be powered to detect if treatment-related change in behavioral activation mediates treatment-related change in depressive symptoms. Therefore, power is based upon the strength of both the 'a' path (i.e., mPEP significantly increases behavioral activation relative to our control condition) and 'b' path (i.e., change in behavioral activation is significantly associated with change in depressive symptoms). As per our pilot data, we conservatively estimate a small-to-medium effect ( $r=.20$ ) between mPEP and behavioral activation ( $r=.20$ ) between mPEP and

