depressive symptoms, and a medium effect ( $r=.50$ ) between change in behavioral activation and change in depressive symptoms. With  $N = 200$  and alpha of 0.05, we have 81% power to detect a significant mediation effect. These power estimates are based on 15% attrition between time-points (39% overall project attrition).

**Hypothesis 3:** Caregivers assigned to the mPEP intervention will show greater reduction in blood pressure relative to those assigned to a web-based bibliotherapy intervention.

Dependent Variables: Systolic and Diastolic Blood Pressure. Independent Variables: Condition and Time (Baseline, 3-, 9-, and 15-months). Moderator: Age.

**Statistical Analysis:** This hypothesis will be tested using GAMMs. Condition will be entered into the model as a fixed-effect predictor along with time and their interaction. Because age is a known predictor of blood pressure we will enter age as a covariate and moderator of treatment efficacy in analyses. If the smoothed interaction of treatment condition and time is significant at the .05 level (determined by an F test of the relevant coefficients in the model) we will test all pairwise differences with Westfall-Young adjusted p values. **Power Analysis:** Power estimates were calculated using the Hedeker, et al. method for various covariance structures for mixed effects models. For the proposed study, we assumed an autoregressive covariance structure. An estimated correlation of 0.4 was assumed between sequential assessments based on our pilot data. Using this methodology, assuming an alpha level of 0.05 and 200 subjects (100 per treatment arm), and 15% attrition between time-points (39% cumulative dropout across time-points), we have 80% power to detect a small-to-medium effect size of 0.32.

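### The H1 and H3 condition-by-time gate neither constrains nor adjusts for baseline; doing so would raise its power, by an amount that depends on effect shape and correlation

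*Combined protocol and SAP*

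**What the plan says.** Under Hypothesis 1 the independent variables are "Condition and Time (Baseline, 3-, 9-, and 15-months"), so baseline is a level of Time rather than a covariate. The model is given as "Condition will be entered as a fixed-effect predictor along with time and their interaction". Pairwise differences are tested only under a condition: "If the smoothed interaction of condition x time is significant at the .05 level".

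Hypothesis 3 has the same structure for blood pressure: "Condition will be entered into the model as a fixed-effect predictor along with time and their interaction", with the gate "If the smoothed interaction of treatment condition and time is significant at the .05 level". The only covariate it names is age.

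The general Statistical Analyses paragraph defines the analysis set as "data included for all subjects completing at least one post-baseline assessment". It admits covariates by a between-arm significance rule and by AIC. Nowhere are the arm means held equal at baseline, and nowhere is the baseline outcome named as a covariate.

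The H1 power paragraph supplies the inputs used below: "we assumed an autoregressive covariance structure, with a correlation between sequential assessments set at 0.5 based on our previous trial in caregivers", and "we have a minimum 90% power to detect an effect size of 0.4 with 15% attrition between each time-point". The H3 paragraph gives a correlation of 0.4, an effect of 0.32 and 80% power.

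**The concern.** With a condition main effect in the model and baseline among the outcome times, each arm has its own baseline mean. A null interaction then says that the arm difference at every later visit equals the difference at baseline. The gate is therefore a comparison of changes from baseline. The plan does not say this outright; it follows from the listed terms.

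In a randomised trial the expected baseline difference is zero, so estimating it freely adds noise to every post-baseline contrast. Under the plan's assumed covariance the correlation with baseline fades quickly, and change scores are then inefficient. The gate decides whether any H1 or H3 pairwise test is done, including those on the primary outcome (depressive symptoms). Power lost there is lost for everything downstream.

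**Working it through.** **Inputs from the documents.** Two-sided alpha 0.05; 100 per arm; 15% loss per interval; autoregressive correlation 0.5 with effect 0.4 (H1), and 0.4 with effect 0.32 (H3).

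**Inputs assumed.** SD 1 (effects are standardised), monotone dropout, known covariance, a stated effect shape, and an unsmoothed 3-df test standing in for the GAMM smooth, whose basis and degrees of freedom are not given.

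**The plan's own figures.** Cumulative dropout is 1 − 0.85³ = 0.386, the stated 39%. A time-averaged arm difference over the three post-baseline visits, ignoring baseline, gives about 90% for H1, as stated, and about 77% for H3 against the stated 80%. Nothing below relies on this.

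**Records per arm.** 100 × 0.85 = 85 at month 3, 72.25 at month 9, 61.41 at month 15. Removing participants with baseline only leaves 85 at baseline.

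**Month 3 by hand (H1, ρ = 0.5).** Variance of the arm difference:
- Free baseline (change): 2 × 2(1 − ρ)/85 = 2/85 = 0.0235.
- Equal baseline means: 2(1 − ρ²)/85 = 1.5/85 = 0.0176.

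The gap widens later. At month 9 the correlation with baseline is 0.25, so the per-person variance is 2(1 − 0.25) = 1.5 for change against 1 − 0.25² = 0.94 adjusted. At month 15 (correlation 0.125) it is 1.75 against 0.98.

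**Joint 3-df gate.** Let V be the GLS covariance of the four arm differences, V = 2(Σ nₖSₖ⁻¹)⁻¹ over dropout patterns, and d the post-baseline effects.
- Free: λ = d′(CVC′)⁻¹d, with C = [−1 | I₃].
- Constrained: λ = d′(Vpp − Vp0V0p/V00)⁻¹d.
- Power = P(χ²₃(λ) > 7.815).

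Flat effect:
- H1: λ = 7.44 free, 12.63 constrained; power 0.619 and 0.860.
- H3: λ = 4.12 and 8.11; power 0.369 and 0.661.

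If baseline-only participants are kept, the free figures rise to 0.647 and 0.394; the constrained figures do not change.

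**Effect shape (H1, AR(1) 0.5, 3-df).**

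| Arm difference at 3/9/15 months | Free | Constrained | Gain, points |
|---|---|---|---|
| .4/0/0 | .781 | .804 | 2 |
| .4/.2/0 | .677 | .736 | 6 |
| 0/0/.4 | .495 | .558 | 6 |
| 0/.2/.4 | .366 | .489 | 12 |
| linear in months to .4 | .310 | .480 | 17 |
| .4/.4/.2 | .635 | .804 | 17 |
| .4/.4/.4 | .619 | .860 | 24 |
| .2/.4/.4 | .407 | .668 | 26 |

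**Other correlations (H1, flat effect, 3-df).** AR(1) 0.7: .830 to .921. AR(1) 0.8: .951 to .976. Compound symmetry 0.5: .743 to .915. Compound symmetry 0.7: .934 to .977. At AR(1) 0.8 with .4/.4/.2 the gain is under 1 point (.970 to .979).

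**Other stand-ins (flat effect, simulated).** With AR(1) estimated by REML and a 3-df F test: .611 to .856 (H1) and .372 to .660 (H3). With a penalised-spline interaction whose critical value is calibrated to 5%: .503 to .828 (H1, about 33 points) and .293 to .652 (H3).

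**If the analysed arms are not equal at baseline.** A true 0.1 SD difference at every visit gives a gate size of .072 (H1) or .079 (H3) constrained, against .050 free. A 0.1 SD shift at baseline alone gives .058 constrained against .079 free (H1), and .055 against .075 (H3).

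**The case against.** The free-baseline model is valid and recognised. It is also the more robust choice when the arms differ by the same amount at every visit. Randomisation does not fully guarantee equal baselines here. Randomization Procedures places allocation after consent without placing the baseline assessment before it, Assessments says only that the first measurement precedes the intervention, and the analysis set drops participants with no follow-up after they were randomised. This stands, and it is why the fix carries a condition.

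The size of the gain rests on a shape that the documents do not give. A fading effect is plausible, since the check-in calls last only three months, and then the gain is small. This also stands. A reader might infer a gain of at least 17 points under the plan's own covariance; that holds only for sustained, growing or half-maintained effects. The smooth matters too: if it collapses to a straight line while the effect fades, constrained power can be slightly lower (.077 to .051 at compound symmetry 0.5, both near alpha).

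The between-arm significance rule or AIC might bring baseline into the model or drop the condition effect. Either would depend on the data and would not be a pre-specified handling of baseline, so this does not answer the point.

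A reader might also take the gap between the stated 90% and 80% and the gate's power as proof of a baseline-handling error. The documents do not support that. The gap concerns which test was powered, and the H1 figure can be reached with no use of baseline at all.

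**Conclusion.** The point holds as an efficiency gain from data already collected, not as an error: the free-baseline gate keeps its 5% size when the arms are truly alike. Under the plan's inputs and a flat effect, constraining baseline moves the 3-df gate from 62% to 86% (H1) and from 37% to 66% (H3). Over the non-negative shapes tried for H1 the 3-df gain is about 2 to 26 points. It is about 33 points for a flat effect with the spline stand-in, and 1 point or less is possible at higher correlation.

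These figures rest on the assumed shapes, monotone dropout, stand-ins for an unspecified smooth, and equal baseline means in the analysed arms. It would be wrong to infer that the change restores the stated power: even for a flat effect the constrained 3-df gate reaches 86% and 66%, short of 90% and 80%.

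**What to change.** For each H1 and H3 outcome, constrain the arm means to be equal at baseline, or enter the baseline value as a covariate. Define the gate as the joint test of the arm differences at months 3, 9 and 15. State that baseline is completed before allocation is known. If that cannot be confirmed, or if early dropout differs by arm, report the free-baseline model as a sensitivity analysis.

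The cost is SAP wording; no new data are needed. The downside is the size inflation to about .07 to .08 if the arms truly differ by 0.1 SD at every visit, which the timing statement and the sensitivity analysis are there to address.

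### The stated 90% and 80% power names no contrast or time pattern; if 0.4 and 0.32 are the differences reached and effects are sustained or rising, the deciding interaction test has about 30-62% and 19-37%

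*Combined protocol and SAP*

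**What the plan says.** Under Hypothesis 1, the model contains condition, time and their interaction, and pairwise differences are tested "If the smoothed interaction of condition x time is significant at the .05 level", judged by an F test. Hypothesis 3 (blood pressure) has the same rule: "If the smoothed interaction of treatment condition and time is significant at the .05 level". The general Statistical Analyses paragraph lets the data set the smoothness of the model terms, so the degrees of freedom of the interaction are not fixed. It describes the analysis as "intent-to-treat with data included for all subjects completing at least one post-baseline assessment".

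The Hypothesis 1 power paragraph reports that "we powered our study based results showing an effect size of 0.4 (small to moderate) in favor of mPEP with an active comparator", assumes an autoregressive structure "with a correlation between sequential assessments set at 0.5 based on our previous trial in caregivers", and concludes that "we have a minimum 90% power to detect an effect size of 0.4 with 15% attrition between each time-point", with 100 participants per condition. For Hypothesis 3: "An estimated correlation of 0.4 was assumed between sequential assessments based on our pilot data", and, again with 100 per arm and 15% attrition per interval, "we have 80% power to detect a small-to-medium effect size of 0.32".

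Neither paragraph says which contrast was powered, at which visit or in what time pattern the effect occurs, which SD standardises it, or how many degrees of freedom the test has. The Hedeker method is cited, but no contrast is named.

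**The concern.** Condition is also a main effect, so the interaction test responds only to change over time in the between-arm difference. Any part of the difference that can be absorbed into a constant is lost to it. Power calculated for an average difference between arms therefore does not carry over to this test.

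At stake is how a negative result is read. If 0.4 and 0.32 are the differences reached, and the effect is sustained or rising, the deciding test would miss it in about 38-70% of trials (Hypothesis 1) or 63-81% (Hypothesis 3), not in 10% or 20%. The pairwise tests would then not be run. A reader who trusted the stated power would take the null result as strong evidence against an effect of that size. If another effect was meant, readers need it to know what the trial is powered for.

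**Working it through.** **Inputs from the plan.** Two-sided alpha 0.05; 100 per arm; adjacent correlation 0.5 (Hypothesis 1) or 0.4 (Hypothesis 3), autoregressive; 15% loss per interval; visits at 0, 3, 9 and 15 months. Numbers seen per arm are 100, 85, 72.25 and 61.4. Cumulative loss is 1 - 0.85³ = 38.6%, matching the plan's 39%. The analysis set drops the 15 per arm with no post-baseline visit.

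**Assumptions not in the plan.** Time patterns; unit between-subject SD as standardiser; fixed 1, 2 or 3 degrees of freedom (linear in months, quadratic in months, visit as category) in place of the data-determined smooth. No multiplicity adjustment is counted.

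**Method.** Let d be the four true between-arm differences, and J half the per-arm information, summed over dropout groups. At 3 df the noncentrality is λ = min over a of (d - a·1)ᵀ J (d - a·1), where a is the constant absorbed by the condition main effect. At 2 or 1 df, λ is the part of this captured by the quadratic or straight line. Power is P(χ²(df, λ) > critical value) for the upper figure of each pair below, and the noncentral F with 166 denominator df for the lower.

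**Recovering the stated figures.** For the mean of the three follow-up visits, with baseline constrained equal and a constant effect from 3 months:
- Hypothesis 1: SE 0.1179, z = 0.4/0.1179 = 3.39, power Φ(3.39 - 1.96) = 92.4%.
- Hypothesis 3: SE 0.1160, z = 0.32/0.1160 = 2.76, power 78.8%.

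These are close to 90% and 80%, but this contrast is not the deciding test.

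**Interaction test, effect sustained from 3 months, 3 df.**
- Hypothesis 1: 56.67a² + 56.67a(0.4 - a) + 78.94(0.4 - a)² = 12.63 - 40.48a + 78.94a². The minimum, at a = 0.256, is λ = 7.44. Against the critical value 7.81, power is 61-62%.
- Hypothesis 3: 50.60a² + 40.48a(0.32 - a) + 79.24(0.32 - a)² = 8.11 - 37.76a + 89.36a². The minimum, at a = 0.211, is λ = 4.12; power 36-37%.

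Leaving the baseline difference free takes λ from 12.63 to 7.44 and from 8.11 to 4.12.

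**Sustained and rising patterns (power, %, at 3 / 2 / 1 df).**

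| Pattern (final size 0.4 or 0.32) | Hypothesis 1 | Hypothesis 3 |
|---|---|---|
| Sustained from 3 months | 61-62 / 48-49 / 32 | 36-37 / 30 / 21 |
| Half at 3 months, full at 9 and 15 | 40-41 / 46-47 / 43-44 | 25 / 29 / 29 |
| Linear by visit | 30 / 34-35 / 43 | 19 / 22 / 28 |

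A simulation with random dropout, the same exclusion and an estimated autoregressive correlation (2,500 runs per case) gave 60, 38 and 29% (Hypothesis 1) and 36, 25 and 18% (Hypothesis 3) at 3 df, with 4.6% rejection under the null. Keeping baseline-only participants adds 1-3 points at 3 df and up to about 4 at 1-2 df. The Assessments paragraph can be read as visits at 0, 3, 6 and 12 months; the overall ranges are then unchanged.

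**Non-sustained patterns.** An effect at 3 and 9 months only gives the highest values: 79-81% (Hypothesis 1) and 49-53% (Hypothesis 3) at 2-3 df. An effect at 9 months only gives 70-71% for Hypothesis 1 at 3 df. A fading effect (full, half, quarter) gives 61-62 / 29 / 5% for Hypothesis 1 and also falls to 5% at 1 df for Hypothesis 3.

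**Other meanings of the effect size.**
- *Four-visit average, widening from zero.* Linear by visit, the 15-month difference is 2 × 0.4 = 0.80 or 2 × 0.32 = 0.64. Linear in months, the mean visit time is 27/4 = 6.75, so it is 0.4 × 15/6.75 = 0.89 or 0.32 × 15/6.75 = 0.71. Power at 3 df is 87-88% (by visit) or 94-95% (in months) for Hypothesis 1, and 65-66% or 76-77% for Hypothesis 3. At 1 df it is 94-95% or 98%, and 79% or 89%.
- *Units of baseline-to-15-month change SD.* That SD is √(2(1 - 0.5³)) = 1.32 or √(2(1 - 0.4³)) = 1.37, so the effects are 0.53 and 0.44 between-subject SD. Power over the three sustained or rising patterns and 1-3 df is 50-87% and 34-64%.

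**The case against.** The strongest reply is that no arithmetic error has been shown. That stands. A reader might infer that 90% and 80% are miscalculated, but the documents do not support this: a baseline-constrained mean follow-up difference comes close to both. So does one form of the interaction. If 0.4 and 0.32 are four-visit averages of a difference widening linearly by visit, then before the analysis-set exclusion the test has about 90% at 3 df for Hypothesis 1, and about 96% and 82% at 1 df. However, the plan nowhere states differences of 0.80-0.89 or 0.64-0.71 SD at 15 months, and it calls 0.4 small to moderate. Even then, Hypothesis 3 at 3 df reaches only about 65-77% after the exclusion.

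A second reply is that 30-62% and 19-37% might be taken as the power for any effect of the stated size. They are not: they cover sustained or rising effects only. Other shapes are plausible here, since coaching calls end after three months and the last visit falls after the intervention. The non-sustained ranges above come from selected patterns. A zigzag effect, present at 3 and 15 months but absent at 9, would give Hypothesis 1 about 91% at 3 df, but it is not a credible treatment profile.

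Third, the planned smooth model with covariance chosen by AIC was not itself evaluated; fixed degrees of freedom and the autoregressive structure are a proxy. Under compound symmetry the shortfall is smaller: an effect starting at 9 months and held gives about 81% at 3 df for Hypothesis 1, against about 51% for Hypothesis 3 after the exclusion. The plan's power calculation, however, assumes an autoregressive structure.

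**Conclusion.** The point holds in a conditional form. The power statements cannot be checked against the test that decides, because its contrast, time pattern, standardiser and degrees of freedom are missing. On the plain reading, with 0.4 and 0.32 as the between-arm differences reached in between-subject SD, that test falls well short of 90% and 80% for every sustained or rising pattern checked at 1, 2 or 3 df. A mismatch between the powered quantity and the deciding test is the likeliest explanation, but the documents do not prove it.

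The size of the shortfall rests on the assumed time patterns and degrees of freedom and on the plan's autoregressive structure. The finding does not show that 200 participants is the wrong number, nor that the interaction test must be abandoned.

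**What to change.** Keep N = 200.

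1. State the contrast, time pattern, standardiser, visit months and interaction degrees of freedom behind 0.4 and 0.32.
2. Replace 90% and 80% with the power of the interaction test under those assumptions, in the plan's own analysis set. If 0.4 and 0.32 are the differences reached, report about 30-62% and 19-37%, labelled as applying to sustained or rising effects only.

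Both steps need one recalculation and SAP wording, with no extra participants or data.

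As an option for the sponsor, not a required correction, the deciding test could be a pre-specified mean follow-up difference with baseline constrained equal or used as a covariate. Its power is about 92% / 79% (Hypothesis 1 / Hypothesis 3) for a sustained effect, 81% / 63% for half at 3 months and 62% / 45% for linear by visit. The price, for Hypothesis 1 against the 3-df interaction test, is lower power for an effect at 15 months only (20% v 49%), at 9 months only (20% v 70%) and for a fading effect (51% v 61-62%).

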***Caregiver Stress:*** Stress will be assessed using the short form of the Zarit Burden Interview (ZBI), which consists of 12 items asking caregivers to rate stress specifically associated with being a caregiver. The has excellent reliability and validity in caregiver populations. Daily stress will be assessed using the Role Overload scale and will be administered via the mPEP program. The Role Overload scale consists of 4 items in which participants are asked to rate the extent to which they feel globally overloaded by life responsibilities. This scale will be administered at baseline, 3-, 9-, and 15-months.

***Care Recipient Functioning.*** We will assess multiple aspects of care recipient (patient) functioning including

cognitive status, problem behaviors, and problems with daily functional tasks (i.e., ADLs and IADLs). To assess patient cognitive functioning, we will utilize the Clinical Dementia Rating (CDR) scale. This scale is administered to the caregiver only, and is a report of the caregivers experience regarding their loved one's cognitive functioning. The CDR will be administered at baseline and 15 months only. ADLs and IADLs will be assessed using the Activities of Daily Living Questionnaire (ADLQ). This scale consists of 28 items, administered to the caregiver, asking about their loved-one's functioning in 6 domains. This scale will be administered at baseline, 3-months, 9-months, and 15-months. Problem behaviors of patients will be assessed using the Revised Memory and Behavior Problem Checklist (RMBPC). This scale will be administered at baseline, 3-months, 9-months, and 15-months.

**Randomization Procedures:** Once the candidate is eligible, willing to participate, and signs our consent form, he/she will be randomly assigned to one of the two intervention groups via a randomization table.

**Interventions:** As described above, participants will be randomized to one of two intervention conditions. Below are descriptions of the two conditions.

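### The activation-to-outcome path in Hypothesis 2 is not protected by randomisation, and the plan names no adjustment set aimed at common causes of activation and mood

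*Combined protocol and SAP*

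**What the plan says.** Under Randomization Procedures, each participant "he/she will be randomly assigned to one of the two intervention groups via a randomization table". Condition is the only thing assigned at random.

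Under Hypothesis 2, Statistical Analysis, "For this hypothesis, multilevel (mixed) models will be used". Four relationships are examined: condition with outcome, condition with activation, "c) the relationship between behavioral activation and the outcome", and condition with outcome given the mediator. Then "Mediation will be tested using the Monte Carlo Method for Assessing Mediation (MCMM"). The section names no covariates, no time order between mediator and outcome, and no sensitivity analysis for confounding.

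The general Statistical Analyses paragraph has two rules on covariates: "Models will include as covariates variables that differ significantly by condition", and "We will use Akaike Information Criterion (AIC) to determine covariance structures and variable selection". No candidate variables are listed for the second. The pattern-mixture analyses in that paragraph concern missing data. Hypothesis 3 does name a covariate for a substantive reason: "Because age is a known predictor of blood pressure we will enter age as a covariate and moderator of treatment efficacy in analyses". Hypothesis 2 has no counterpart.

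Under Measures, Care Recipient Functioning, "Problem behaviors of patients will be assessed using the Revised Memory and Behavior Problem Checklist (RMBPC"). RMBPC and ADLQ are collected at baseline, 3, 9 and 15 months, and the CDR at baseline and 15 months only. None of the three appears in any model.

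**The concern.** Randomisation protects the effect of condition on activation (the a path) and on the outcome. It does not protect the relation of activation to outcome (the b path), because caregivers largely determine how active they are. A caregiver whose relative becomes harder to manage may do fewer pleasant activities and also feel worse. That pattern looks like a benefit of activation even if there is none. The app also sets each week's activity goal partly from mood, so earlier mood can shape later activity in the mPEP arm.

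The arm-difference rule does not address this. Under randomisation it picks any given baseline variable about 5% of the time, however strongly that variable confounds the b path. At stake is the Aim 2 claim about mechanism: a significant indirect effect could not be told apart from less burdened caregivers both doing more and feeling better.

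**Working it through.** **Inputs from the plan.** a = .20 (mPEP with activation), b = .50 (change in activation with change in depressive symptoms), N = 200, two-sided alpha 0.05, 15% attrition per interval. Retained at 15 months: 200 × 0.85³ = 122.8, taken as 122.

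**Input not in the plan.** g, the correlation of a common cause U with activation, taken as equal in size to its correlation with the outcome. The documents give no value; the range 0 to .5 is an assumption.

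**The plan's own figure.** Joint power is the product of Φ(atanh(r)·√(N−3) − 1.96) over the two paths.
- N=200, a path: 0.2027 × 14.04 = 2.845; Φ(0.885) = .812. The b path is about 1. Joint: 81.2%, matching the stated 81%.
- N=122, a path: 0.2027 × 10.91 = 2.212; Φ(0.252) = .599. Joint: about 60%.

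So the 81% matches full retention, although the text says it allows for attrition. That is a separate matter, but it is why both sample sizes are shown below.

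**False mediation.** Set the true b to 0 and keep a = .20. With X the condition, M = .20·X + g·U + error and Y = g·U + error, all with unit variance. (Reversing the sign of Y gives the harmful-decline case; the rates are the same.) Omitting U gives an apparent b of g²/(1 − .20²) = g²/.96, which is .094, .167 and .260 at g = .3, .4 and .5. The partial correlation is g²/√.96 = .092, .163 and .255.

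Hand approximation at N=200: Φ(atanh(partial r)·√196 − 1.96) × .812.
- g=.3: Φ(1.290 − 1.96) × .812 = .251 × .812 = 20%
- g=.4: Φ(2.307 − 1.96) × .812 = .636 × .812 = 52%
- g=.5: Φ(3.654 − 1.96) × .812 = .955 × .812 = 78%

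Simulation of the Monte Carlo interval for a×b, 2,000 trials per cell, percent declaring mediation:

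| g | N=200, arm-difference rule | N=200, U always adjusted | N=122, arm-difference rule | N=122, U always adjusted |
|---|---|---|---|---|
| 0 | 3.7 | 2.9 | 2.0 | 2.4 |
| .2 | 5.7 | 3.8 | 4.0 | 2.6 |
| .3 | 17.6 | 3.3 | 8.4 | 2.4 |
| .4 | 48.8 | 3.2 | 25.6 | 3.3 |
| .5 | 74.4 | 3.0 | 43.2 | 3.8 |

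The rule selected U in about 4-5% of trials. Repeat runs gave up to 48% in the g=.5, N=122 cell. If U is measured with reliability .8, adjusting for it at N=200 leaves 4.4%, 7.1% and 12.0% at g = .3, .4 and .5.

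**Adding the first of the four conditions** (condition-outcome effect significant), N=200, g = .3, .4, .5:
- no benefit by any other route: 1.2%, 2.0%, 3.6%;
- a direct effect of .20 by another route: about 16%, 41%, 65%. A repeat run gave about 18% to 68% over this range, and 6% to 31% at N=122.

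**AIC.** One added term is kept if its likelihood-ratio statistic exceeds 2, that is |z| > 1.414. For g=.3 at N=200: Φ(0.3095 × 14.04 − 1.414) = Φ(2.93) = 99.8%. At N=122: Φ(0.3095 × 10.91 − 1.414) = Φ(1.96) = about 97%. This applies only if the variable is offered as a candidate.

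These are single-level models with one mediator and one outcome value per person, so they indicate the size of the problem in the planned multilevel analysis and do not reproduce it.

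**The case against.** Several points on the other side stand, in whole or part.

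- A reader might infer that the arm-difference rule is the plan's only covariate rule. It is not: AIC selection would very probably keep a strong common cause if offered one. But no candidates are listed, and AIC selects on fit, not on confounding. The protection is possible, not assured.
- A reader might infer that care-recipient decline is fully tracked at every visit. That is true of RMBPC and ADLQ but not of cognition, since the CDR is given twice.
- A reader might take the highest rates as what the trial should expect. The documents do not support that. Confounder strength is assumed, the rates are lower at N=122, and a required condition-outcome effect nearly removes the problem when mPEP has no other benefit. However, the plan does not say that all four conditions must hold, and a coached programme could help by another route.
- Hypothesis 2 is framed on change, which largely removes stable differences between caregivers. The confounder then has to be a change in circumstances related to both changes, which may make .3 or more less likely. The documents do not settle this.
- Adjusting for post-baseline RMBPC or ADLQ carries its own risk. Both are caregiver-reported and could respond to treatment, and the comparator itself covers problem behaviours. This argues for keeping them out of the primary model.

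**Conclusion.** The point holds as a gap in specification with a possible material effect on Aim 2. The activation-outcome path is observational, the arm-difference rule is aimed at the wrong variables, and nothing else in the plan assures adjustment for common causes.

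The size is conditional on a true b of 0, a = .20 and a single common cause of assumed strength. At .3 to .5, false mediation is about 18-75% at N=200 and 8-48% at N=122; at .2 it is about 4-6%. With the condition-outcome requirement it is about 1-4%, or about 16-68% at N=200 and 6-31% at N=122 if mPEP also works by another route. The return to under 5% assumes that the cause itself is adjusted for and measured without error.

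It does not follow that a mediation finding would be false, or that the efficacy result is in doubt. Hypothesis 1 compares randomised arms and does not use this path. The change is recommended for the mechanism claim.

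**What to change.** For the Hypothesis 2 mediator and outcome models:

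1. Replace the arm-difference rule with pre-specified adjustment for baseline CESD-R (or the baseline value of whichever outcome is analysed), baseline RMBPC and baseline ADLQ. Add baseline activation where it is available in both arms. The Measures section lists no activation scale and Aim 2 draws engagement from the portal, so availability needs checking.
2. Relate activation to the outcome at a later visit.
3. State whether all four conditions must be met before mediation is claimed.
4. As sensitivity analyses, adjust for RMBPC and ADLQ at the preceding visit, noting that treatment may affect them. Report how strong an unmeasured confounder would have to be to remove the indirect effect.

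The cost is SAP wording, a few degrees of freedom and a little more analysis; the CESD-R, RMBPC and ADLQ data are already collected. Baseline adjustment alone does not remove confounding by later care-recipient decline, so statements about mechanism should remain conditional on the sensitivity analyses.
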